##### **4.5.2.1.1. Immune-related Adverse Events (irAEs)**

irAEs will be graded by the investigator according to the National Cancer Institute-Common Terminology Criteria for Adverse Events (NCI-CTCAE), Version 5. irAE will be coded using the standard Medical Dictionary for Regulatory Affairs (MedDRA dictionary, version 25.0) and grouped by SOC.

A summary of all immune-related adverse events by system organ class, preferred term and maximum grade, and a listing containing all immune-related adverse events will be produced.

#### **4.5.2.2. COVID-19 Assessment and COVID-19 AEs**

A Standardised MedDRA Query (SMQ) will be used to identify all COVID-19 AEs.

The impact of COVID-19 on DLTs during the DE phase of any sub-study will be monitored during the study conduct through review of protocol deviations. DLTs will be reported according to the DLT evaluable population in Section 3 of the MSAP.

The incidence of AEs and SAEs (Fatal and Non-Fatal) of COVID-19, COVID-19 AEs leading to study drug discontinuation, and COVID-19 AEs leading to study withdrawal, and COVID-19 AEs by severity, will be obtained from standard AE and SAE summaries and listings.

#### **4.5.2.3. Deaths and Serious Adverse Events**

Refer to Section 4.5.2.4 of the MSAP.

#### **4.5.2.4. Adverse Events Leading to Discontinuation of Study Treatments and Other Significant Adverse Events**

The following categories of AEs will be summarized separately by individual treatment component and combination (belantamab mafodotin monotherapy and GSK'998 (aOX40) + belantamab mafodotin) as collected in descending order of total incidence by SOC and PT and separate supportive listings will be generated with participant level details for those participants:

- AEs Leading to Permanent Discontinuation of Study Treatment
- AEs Leading to Dose Interruptions or Delays
- AEs Leadings to Dose Reductions

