**Table 10 Permitted dose reductions for Belantamab mafodotin when in combination with GSK'998 (aOX40)**

Belantamab mafodotin Dose Level	1st Dose Reduction
2.5 mg/kg	1.9 mg/kg
1.9 mg/kg	-

- The dose of GSK'998 (aOX40) will not be modified. Please refer to Section 2.3.
- If the participant cannot tolerate the drug after the allowed dose reductions, he or she must be withdrawn from the study for lack of tolerability.
- Only one dose reduction of belantamab mafodotin (to 1.9 mg/kg) is permitted from any 2.5 mg/kg belantamab mafodotin dose level in Table 10.

- No dose reduction of belantamab mafodotin is permitted from the starting dose level of 1.9 mg/kg as lower doses are likely to be inefficacious based on findings from Part 1 of the FTIH trial (GSK Study BMA117159).
- In case of full resolution of symptoms which lead to dose reduction, further treatment with belantamab mafodotin at the initially-assigned dose may be considered by the investigator.
- Resuming treatment with belantamab mafodotin may be possible after the toxicity has resolved to Grade 1 or less.
- If GSK'998 (aOX40) is permanently withdrawn the participant can remain on belantamab mafodotin, if belantamab mafodotin is permanently withdrawn the participant will be withdrawn from all study treatment.

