## 1. INTRODUCTION

The purpose of this SAP is to describe the planned analyses to be included in the CSR for Study 208887 sub-study 1. For more details about the statistical analysis and plan for the overall study refer to the Master SAP. This sub-study was terminated early in the Dose Exploration (DE) phase; therefore, this sub-study SAP will focus only on this DE phase.

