##### 4.1.2.1. Study Treatment & Sub-group Display Descriptors

Phase	Description
DE	1.9mg/kg GSK916+8mg aOX40
	2.5mg/kg GSK916+8mg aOX40
	2.5mg/kg GSK916+24mg aOX40 

 Note that this dose level was not used due to early termination

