#### **4.5.1. Extent of Exposure**

Refer to the Master SAP Section 4.5.1 for details on the extent of exposure for this study. The cycle length term Q3W is equivalent to a cycle length in days of 21 days, to be used in calculations for treatment exposure.

Extent of exposure to belantamab mafodotin monotherapy and combination therapy will be summarized. For the combination therapy, extent of exposure will be summarized.

A 'by participant' summary listing of data on exposure to all study treatments will be produced.

Dose reductions will be summarised by number of reduction and reasons for reductions. Dose delays/interruptions will be summarised by number of delays, and delay duration (days). All the dose reductions and dose delays/interruptions will be listed.

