### **5. SAMPLE SIZE DETERMINATION**

In the DE phase, approximately up to 10 participants will be assigned to the combination dose level. However, the study was terminated early due to lack of efficacy; therefore only 6 participants were enrolled onto dose 1 and 3 participants were enrolled onto dose 2.

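### Does a leftover monotherapy label in the exposure and AE-action tables hide how GSK'998 was tolerated?

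*SAP*

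**What the plan says.** The SAP was written after the sub-study had closed, and section 1 limits its scope: "this sub-study SAP will focus only on this DE phase". The display descriptors in section 4.1.2.1 are all combinations, beginning with "1.9mg/kg GSK916+8mg aOX40". Section 5 gives the enrolment: "only 6 participants were enrolled onto dose 1 and 3 participants were enrolled onto dose 2".

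Two places nevertheless speak of monotherapy.

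- Section 4.5.1: "Extent of exposure to belantamab mafodotin monotherapy and combination therapy will be summarized". The same section opens with "Refer to the Master SAP Section 4.5.1 for details on the extent of exposure for this study" and adds "A 'by participant' summary listing of data on exposure to all study treatments will be produced". It also plans summaries and listings of dose reductions and delays.
- Section 4.5.2.4: three kinds of adverse event (those leading to permanent discontinuation, to interruption or delay, and to reduction) are to be "summarized separately by individual treatment component and combination (belantamab mafodotin monotherapy and" the combination). The sentence goes on to say that this follows the data as collected, and that separate supporting listings will show the participants concerned.

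On the treatment rules, Protocol section 6.6.1 says that if GSK'998 "is permanently withdrawn the participant can remain on belantamab mafodotin". Section 6.6.2 lets GSK'998 be delayed without moving the belantamab mafodotin schedule, and allows no change to the GSK'998 dose.

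**The concern.** A comparison with belantamab mafodotin monotherapy belonged to cohort expansion (Protocol section 1.1), and SAP section 1.1 cancels all analyses of that phase. A monotherapy category in a DE-only plan therefore has no enrolled group behind it. The SAP does not define the term, and it can be read in three ways:

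- an empty column;
- belantamab-only cycles given after GSK'998 was withdrawn, a group formed by what happened on treatment;
- the belantamab mafodotin component of the combination.

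The second reading would put a selected subset beside the combination and invite a comparison with no basis in the design.

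Meanwhile GSK'998, the drug being added, is missing from the parenthesis. If an adverse event led to stopping or holding only GSK'998, and the tables offered only belantamab monotherapy and the combination, the event would go under the combination and the reader could not tell which drug had to be stopped. In a phase whose primary objective is the safety and tolerability of the pair, that information matters.

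**Working it through.** The plan states no figure on this point, so the check is a count and a comparison of sections.

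**Is there a monotherapy group?** Section 4.1.2.1 lists 3 descriptors, of which 0 are monotherapy. Enrolment in section 5 is 6 + 3 = 9, all at combination dose levels. Participants assigned to monotherapy: 0 of 9. The label has no assigned group behind it.

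**Where can the two drugs differ?** Protocol sections 6.6.1 and 6.6.2 give:

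| Action | GSK'998 only | Both drugs | Belantamab mafodotin only |
|---|---|---|---|
| Permanent discontinuation | possible | possible | not possible: withdrawing belantamab mafodotin ends all study treatment |
| Delay | possible | possible | not possible: a belantamab mafodotin delay also delays GSK'998 |
| Reduction | not possible: no GSK'998 dose change allowed | not possible | possible from 2.5 mg/kg |

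GSK'998-specific entries can thus arise in 2 of the 3 AE-action tables. For those two, action on GSK'998 alone is the only way in which the drugs can part, so the omission from the parenthesis is not trivial on its face.

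**What does the sentence in 4.5.2.4 instruct?** Its rule is reporting by component and by combination. The components are belantamab mafodotin and GSK'998 (Protocol section 6.1, Table 8), so the rule implies three categories: each drug and the pair. The parenthesis names two. Rule and parenthesis disagree, and nothing in the SAP says that GSK'998 is excluded or that its events go into the combination category.

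**What is reported whichever reading is taken?**

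- Dose-limiting toxicities and adverse events, summarised and listed (SAP 4.2).
- All, drug-related and serious adverse events, and those leading to permanent discontinuation, in tables by event term and worst grade (SAP 4.5.2).
- Immune-related adverse events, the class that Protocol Table 11 sets out for GSK'998, in their own table and listing (SAP 4.5.2.1.1).
- Exposure to every study drug, listed by participant; reductions and delays, summarised and listed (SAP 4.5.1).
- Listings of the participants behind each AE-action table (SAP 4.5.2.4).

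**How large could the effect be?** Under the least favourable reading, with k participants stopping GSK'998 alone, the table would show 0 such stops instead of k. The documents do not give k. If k = 1 is assumed, the missing entry is 1/6 = 16.7% of dose level 1 or 1/3 = 33.3% of dose level 2. These percentages are one person over a very small denominator, and they depend on a reading that the rule itself does not support. That person would still appear in the listings.

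**The case for a change.** The strongest case for a change is that the correction is cheap and the tables bear on the primary objective. The drugs can be stopped and held separately, the general discontinuation table in section 4.5.2 does not say which drug was stopped, and a SAP written after closure had every chance to drop a label that belonged to a cancelled phase. A single combination exposure summary could hide the fact that a participant received fewer GSK'998 infusions than belantamab mafodotin infusions.

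Part of this stands. The label is undefined and does not fit DE, and the parenthesis does not match its own sentence.

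The rest does not carry through. The added drug's tolerability is tabulated in several places, so at most the attribution of an action to one drug is unclear in a few tables. The primary endpoints in SAP Table 2 are dose-limiting toxicities, adverse events, and changes in clinical signs and laboratory values; per-drug action tables are not among them. Section 2 states that no hypothesis is tested, and no comparison between columns is specified, so the misleading contrast is a possibility rather than a planned analysis. Section 4.5.1 sends exposure detail to the Master SAP, which is not among the documents reviewed, so it cannot be said that per-drug exposure is unplanned.

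**Conclusion.** This is a clerical leftover in two sections, and it calls for no change. The per-component rule in 4.5.2.4 already covers GSK'998. An analyst facing 9 participants, none assigned to monotherapy, would report action on each drug and would have no separate monotherapy arm to fill. Rewording would change the labels on one exposure summary and the AE-action tables. No estimate, denominator, safety finding or conclusion would move, and with 9 people the listings let a reader follow each participant.

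This rests on two assumptions. The first is that the action taken was recorded separately for each drug, as the SAP's wording suggests; the case report form is not among the documents. If it was not recorded that way, rewording the SAP could not recover it. The second is that the Master SAP does not direct GSK'998 actions into a combined category; nothing in the sub-study documents suggests that it does.

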#### **4.5.2.5. Pregnancies**

Refer to Section 4.5.2.6 of the Master SAP.

#### **4.5.2.6. Clinical Laboratory Analysis**

Refer to Section 4.5.2.7 of the MSAP for more details on the clinical laboratory analysis including the analysis of liver function tests.

Summaries of chemistry changes from baseline, hematology changes from baseline, and hematology/chemistry results by maximum grade increase post-baseline relative to baseline will be produced. Supporting listings of laboratory data and urinalysis data for participants with any value of potential clinical importance will be provided.

#### **4.5.3. Other Safety Assessments**

The analyses of non-laboratory safety test results including ECGs and vital signs will be based on GSK Core Data Standards, unless otherwise specified. LVEF and Performance status will be summarized and listed based on GSK Oncology Data Standard. The details of the planned

displays are presented in the OPS document. For more detail please refer to Section 4.5.3 of the Master SAP.

#### **4.6. Other Analyses**

No POPPK, exploratory biomarker, or PD analyses will be conducted. For this sub-study there will also be no health-related quality of life analysis due to early termination.

##### **4.6.1. Pharmacokinetic Analysis**

PK samples will be collected for belantamab mafodotin and/or aOX40 in Cycle 1 as well as later cycles as indicated in the SoA tables of protocol. PK analyses will be done for each analyte measured in the DE phase, as data permit. For more details on these analyses refer to the Master SAP Section 4.6.1.

##### **4.6.2. Immunogenicity Analysis**

Refer to section 4.6.5 of the Master SAP for more details on the analysis of incidence and titers of ADAs against belantamab mafodotin and its combination with aOX40, when measured.

#### **4.7. Interim Analyses**

The planned interim analysis can be found in more detail in Section 4.7 of the Master SAP.

An interim analysis for ORR would have been performed at the end of the DE phase, after 10 participants had been treated. However, due to the early termination of this sub-study neither of the 2 dose levels explored in this sub-study reached the 10-participant goal. Hence, no interim analysis will be performed.

### **5. SAMPLE SIZE DETERMINATION**

In the DE phase, approximately up to 10 participants will be assigned to the combination dose level. However, the study was terminated early due to lack of efficacy; therefore only 6 participants were enrolled onto dose 1 and 3 participants were enrolled onto dose 2.

### **6. SUPPORTING DOCUMENTATION**

For supporting documentation for this overall study please refer to Section 6 of the Master SAP for more details.

**Trademarks**

Trademarks of the GlaxoSmithKline Group of Companies
Blenrep

Trademarks not owned by the GlaxoSmithKline Group of Companies
MedDRA

